2. OBJECTIVE(S)

2.1. Primary Objective

Characterize the efficacy of a 24-week withdrawal followed by a 28-week reintroduction of intravenous belimumab therapy compared with uninterrupted intravenous belimumab therapy for 52 weeks in subjects with low SLE disease activity receiving belimumab 10 mg/kg plus standard of care, as measured by time to first flare.

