belimumab open-label continuation studies in subjects with SLE (BEL114333; HGS1006-C1066; LBSL99). Subjects will have been treated with belimumab for at least 6 months in one of these continuation studies but will have withdrawn from belimumab therapy for no longer than 8 weeks prior to entry into this study. These subjects may have any level of SLE disease activity. The target enrolment for this group is 35 subjects.

The study consists of a screening phase of up to 30 days, a 52-week treatment/observation phase with an escape option, a maintenance phase, and a follow-up phase. The screening phase will allow an assessment of the SELENA SLEDAI score and complement (C3 and C4) levels as part of the eligibility criteria for subjects in the treatment holiday and control groups. All subjects will attend clinic visits for efficacy and safety assessments every 4 weeks for 52 weeks. At the end of the 52 week period, subjects in the treatment holiday and control groups will have the option to continue belimumab therapy in the maintenance phase of this study only if belimumab is not commercially available in a subject's country of participation. This maintenance phase will last until such time as belimumab becomes commercially available in a subject's country of participation, or the Sponsor discontinues the maintenance phase of the study for China subjects with the provision for China subjects to elect to participate in a different protocol to continue to receive belimumab, or the Sponsor decides to terminate the study. Safety reporting will be as specified in the protocol the subject participates in.

A 16-week follow-up visit will be scheduled for subjects in the treatment holiday and control groups after the withdrawal visit or the last dose of belimumab as appropriate. Additionally, a 6 month follow-up visit is required for those subjects in the treatment holiday or control groups.

Subjects in the treatment holiday group may re-start belimumab therapy prior to Week 24 in the event of a severe SLE flare as per the SLE flare index (Appendix 1). These subjects will then enter the maintenance part of this study by the escape option for ongoing belimumab treatment.

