Subjects in the treatment holiday group are anticipated to be temporarily withdrawn from belimumab treatment for the initial 24 week holiday period of this study but therapy with belimumab 10 mg/kg can be reintroduced before the Week 24 visit if the subject's condition worsens or meets the definition of a severe flare as per the SLE flare index (Appendix 1). Subjects in the treatment holiday group who re-start belimumab treatment before the end of the 24-week holiday period will escape to the maintenance part of this study to receive further belimumab therapy.

The investigator must make every reasonable attempt to re-start belimumab therapy at the Week 24 visit. Any subject in the treatment holiday group who remains off-therapy with belimumab at the Week 24 visit can still be treated with belimumab from Week 28 onwards.

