- 15. Biological Markers include FACS of peripheral lymphocytes: B lymphocytes (CD20+, CD20+/27+ memory, CD20+/27- naïve, CD20+/69+ activated, CD20+/138+ plasmacytoid, CD19+/27^{BRIGHT}/38^{BRIGHT} SLE subset and CD20-/138+ plasma cells). Note: B cell markers will not be collected at the 6-month follow up visit for subjects in the long-term discontinuation group as this visit does not apply to this subject group.
- 16. Only subjects in the control group will receive belimumab 10 mg/kg during Weeks 0 through 20 inclusive; subjects in the control group must be able to receive the first dose of belimumab in this study 4 weeks (minimum of 2 weeks, maximum of 8 weeks) after the last dose in their previous open-label continuation study Subjects in the control group and treatment holiday groups will receive belimumab from Weeks 24 through 48 although subjects in the treatment holiday group may be treated with belimumab prior to Week 24 as determined by the investigator in the event of increased SLE activity. When belimumab therapy is re-started, subjects in the treatment holiday group will remain under clinical supervision for 3 hours after completion of the first 2 infusions. At the Week 52 visit, only subjects in the treatment holiday and control groups who are continuing belimumab therapy beyond this time will be dosed.

2012N154810_06

CONFIDENTIAL

2018N381035_00 BEL116027

Table 3 Time and Events Table (Additional Years)

Study Visit (Weeks) ¹	4	8	12	16	20	24	28	32	36	40	44	48
Study Day	28 ±7d	56 ±7d	84 ±7d	112 ±7d	140 ±7d	168 ±7d	196 ±7d	224 ±7d	252 ±7d	280 ±7d	308 ±7d	336 ±7d
Efficacy Assessments												
Disease Activity Scales: SELENA SLEDAI, SLE Flare Index, and PGA ²						х						Х
SLICC/ACR Damage Index												Х
Safety Assessments												
Symptom-driven Physical Exam						Х						Х
Record Concurrent Medications	Х	Х	Х	Х	Х	Х	Х	Х	Х	Х	Х	Х
Adverse Events	Х	Х	Х	Х	Х	Х	Х	Х	Х	Х	Х	Х
Vital Signs ^{3, 4}	Х	Х	Х	Х	Х	X	Х	Х	Х	Х	Х	Х
Laboratory Assessments												
Haematology & Modified Chem 20 (non- fasting) ^{3, 5}						Х						Х
Urinalysis ^{5, 6}						Х						Х
Spot urine (protein to creatinine ratio) ^{3, 5, 6}						Х						Х
Urine Pregnancy Test ^{3, 5, 7}	Х	Х	Х	Х	Х	Х	Х	Х	Х	Х	Х	Х
C3, C4, Anti-dsDNA Autoantibodies ^{3, 5}						Х						Х
IgG ^{3, 5, 8}												Х
IgA & IgM ^{3, 5, 8}												Х
Exploratory Lab Assessments												
Immunogenicity ^{3,9}						Х						Х
B cell Markers ¹⁰												Х
Investigational Product												

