7.4. Efficacy Data for Maintenance Phase Subject Profile

Flare data will be listed on the subject profile.

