13.4. Appendix 4: Study Phases and Treatment Emergent Adverse Events

13.4.1. Treatment Phases

- Visits, assessments and events will be classified according to the time of occurrence relative to the following cut-point dates for each treatment group.
- For convenience and ease of data presentation, the 52-Week Treatment Phase has the same name designation for all three treatment groups, even though the LTC group does not receive treatment at all during this phase and the TH group receives treatment for only the second half of the phase.
- Only the TC and TH groups are eligible to participate in the Maintenance Phase.
- If an AE start date falls on the Day 0 date, then it will be considered treatment emergent (i.e., fall in the 52-week treatment phase). If a concomitant medication start date falls on the Day 0 visit date, the concomitant medication will be considered to fall in the 52-week treatment phase. Any other assessments that fall on the Day 0 visit date will be considered to occur in the pre-study phase.
- For the TC group, if the first infusion date differs from the Day 0 visit date, then the first infusion date will be used as the phase cut-point.
- Other than Day 0, if an assessment or event occurs on the same date as a phase cutpoint, then the event will be considered to fall in the previous phase. For example, if a new prednisone dose starts on the same date as the Week 24 visit date and then continues for a total of 7 days, then the first day of that prednisone dose will fall into the Holiday Phase and the remaining 6 will fall into the Re-start phase.
- For AEs, if the AE Onset date is missing, then the AE will be considered to occur in the 52-week treatment phase.
- For the TH group, a subject who re-starts treatment prior to Week 24 will not have a Re-Start phase.

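### Re-start Phase summaries describe reintroduction only in holiday subjects who did not re-start belimumab early

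*SAP*

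**What the plan says.** Protocol 2.1 makes reintroduction part of the primary objective: "Characterize the efficacy of a 24-week withdrawal followed by a 28-week reintroduction of intravenous belimumab therapy", compared with uninterrupted therapy and measured by time to first flare.

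A holiday subject may re-start before Week 24. Protocol 3.1 says: "These subjects will then enter the maintenance part of this study by the escape option for ongoing belimumab treatment". Protocol 4.4 agrees that the subject "will escape to the maintenance part of this study to receive further belimumab therapy". SAP 13.4.1 then sets the analysis rule: "For the TH group, a subject who re-starts treatment prior to Week 24 will not have a Re-Start phase".

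From the Escape visit the maintenance calendar applies (SAP 13.3.1). In protocol Table 3 the row "Disease Activity Scales: SELENA SLEDAI, SLE Flare Index, and PGA" is marked only at Weeks 24 and 48. In Table 2 it is marked at every 4-weekly visit.

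On the analysis side:

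- SAP 7 reports holiday-group efficacy separately for the holiday and re-start phases.
- The flare, SELENA SLEDAI and PGA tables in SAP 13.11.5 stop at Week 52 or the 52-week treatment phase.
- For maintenance, SAP 7.4 says: "Flare data will be listed on the subject profile".
- SAP 8.2.1.2 and Table 3.22 summarise post-infusion reactions over the first six infusions of the re-start phase only.
- SAP 13.6.2 sets escapers' treatment compliance to missing.

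**The concern.** A reader of a treatment-holiday study wants to know what happens when the drug is given back, particularly to someone who got worse without it. Under SAP 13.4.1 the subjects re-treated early for worsening are absent, by rule, from the summaries that describe reintroduction: re-start flare rate, SELENA SLEDAI, PGA, prednisone and biomarkers. Their absence depends on outcome, not on chance.

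The same applies to safety on re-exposure. Protocol 6.4.12 asks for the same supervision after the first two re-start infusions whether belimumab is given as rescue or at Week 24. The by-infusion reaction summary covers only infusions in the re-start phase, so rescue re-exposures fall outside the display designed for re-exposure.

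At stake is how far the Re-start results reach. Without a label they can be taken as reintroduction in all re-treated holiday subjects, which they are not.

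**Working it through.** The plan gives no power or error-rate figure to reproduce; it is stated to be descriptive. The check is a count of visits and denominators.

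**The plan's own infusion counts.** Weeks 24 to 48 in 4-week steps: (48 − 24)/4 + 1 = 7. Weeks 0 to 48: (48 − 0)/4 + 1 = 13. Both match the prescribed infusions in SAP 13.6.2 (7 holiday, 13 control).

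**Scheduled flare assessments in the first 28 weeks of re-treatment.**
- Re-start at Week 24 (Table 2): Weeks 28 to 52, (52 − 28)/4 + 1 = 7.
- Escaper (Table 3), taking the Escape visit as the first re-start infusion: one, 24 weeks after escape.
- SAP 13.3.1 notes that the eCRF labels the first visit after escape as Week 8 and re-maps it to Week 4. If sites followed the eCRF labels, the assessments fall about 20 and 44 weeks after escape. That is still 1 within 28 weeks.

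**Denominators.** SAP 2.3 gives 12 enrolled holiday subjects. Each escape removes 1/12 = 8.3% of the group and 28 of 12 × 28 = 336 possible re-treatment weeks. With 1, 2, 3 or 4 escapes, at most 11, 10, 9 or 8 subjects remain in the Re-start Phase. Withdrawals before Week 24 would reduce this further.

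**How likely is at least one escape?** The documents give no number. Assuming an escape probability p of 5% to 40%, the expected number is 12p = 0.6 to 4.8. P(at least one) = 1 − (1 − p)^12, which runs from 0.46 to above 0.99.

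**Effect on the reported flare rate.** Assume that escapers flare after re-start at r times the rate of the others and that k subjects escape. The Re-start rate divided by the rate in all re-treated subjects is 12/[(12 − k) + k·r].

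| k | r = 0.5 | r = 1 | r = 2 | r = 3 |
|---|---|---|---|---|
| 1 | 12/11.5 = 1.04 | 1.00 | 12/13 = 0.92 | 12/14 = 0.86 |
| 3 | 12/10.5 = 1.14 | 1.00 | 12/15 = 0.80 | 12/18 = 0.67 |

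Both r and k are assumed. The direction depends on r, and r = 1 gives no bias.

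**Why flare rates should not be pooled.** SAP 13.6.3 says the SFI reports the first flare since the last assessment, so at most one flare is recorded per assessment. Assume a constant flare rate λ per year. Over 24 weeks the expected recorded number is 6 × [1 − exp(−4λ/52)] with 4-weekly assessment and 1 − exp(−24λ/52) with one assessment.

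| λ (assumed) | True | 4-weekly | One assessment |
|---|---|---|---|
| 0.5 | 0.23 | 0.23 | 0.21 |
| 1 | 0.46 | 0.44 | 0.37 |
| 3 | 1.38 | 1.24 | 0.75 |

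The sparse schedule alone lowers escapers' counts, so a pooled rate would be distorted.

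**The case against.** The strongest defence is that the study is descriptive, the group has 12 subjects, and showing a few escapers individually is a reasonable choice. Their data are not discarded. Flares are listed on subject profiles (SAP 7.4), as are AEs, Grade 3 or 4 laboratory results and immunogenicity (SAP 8.5). B-cells are plotted by subject (SAP 11.2). Listings 43 to 46 cover SFI flares, SELENA SLEDAI, PGA and prednisone with no 52-week limit in their titles. A single late SFI assessment also looks back over the whole interval, so it loses timing and repeat flares but not necessarily whether any flare occurred. All of this stands. It makes the remedy a matter of display and labelling, but it does not give any summary of reintroduction in all re-treated subjects.

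Several stronger readings are tempting, and the documents do not support them:

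- **The primary analysis loses escapers.** It does not. SAP 7.1.4 counts an SFI flare from Day 0 as an event, including one before escape.
- **Everyone who flared is removed, so Re-start results reflect a successful holiday.** Exclusion follows early re-start, not flare. A subject with a mild or moderate flare who stays off drug to Week 24 has a Re-start Phase.
- **Re-start results look better than the truth.** That needs escapers to do worse after re-start. Neither their number nor their outcomes are given.
- **Late re-starters are misclassified.** Protocol 4.4 says a subject "who remains off-therapy with belimumab at the Week 24 visit can still be treated with belimumab from Week 28 onwards". The cut-point in SAP 13.4.1.1 and 13.6.3 names both Week 24 and treatment re-start. The SAP 13.4.1 example using the Week 24 visit date only shows how to split a prednisone course. The wording does not say which date governs when they differ, but no error is shown.

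**Conclusion.** The point holds as a limit on what the Re-start Phase summaries describe. They cover holiday subjects without early re-start, by a stated rule, and no planned summary covers reintroduction in all re-treated holiday subjects. The by-infusion reaction summary has the same gap.

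Each escape costs 8.3% of the enrolled group and leaves 1 scheduled flare assessment in place of 7 over the first 28 weeks of re-treatment, taking the Escape visit as the re-start date. The size and direction of any bias cannot be established. The ratios above rest entirely on assumed values, and with equal post-re-start rates the loss is of information only. This is a cheap improvement to reporting and leaves the primary time-to-first-flare analysis as it is.

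**What to change.** In the SAP:

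1. In 13.4.1 and 13.6.3, define re-treatment time from the first re-start infusion for every re-treated holiday subject, and state that this date governs when it differs from the Week 24 visit. For late re-starters this is a clarification.
2. Add one descriptive display by weeks since re-start, with escapers in a separate column and their assessment frequency stated. Do not pool flare rates across 4-weekly and 24-weekly ascertainment.
3. Include escapers' first six re-start infusions in the by-infusion reaction summary (8.2.1.2, Table 3.22).
4. Report the number of escapes and the Re-start denominators, and label the existing Re-start summaries as limited to subjects without early re-start.

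In the protocol, only if subjects can still be affected: collect SFI, SELENA SLEDAI and PGA at escapers' existing 4-weekly infusion visits for 28 weeks. SAP 2.3 reports final enrolment and SAP 5.3.1 refers to the last patient's last visit in the past tense, so this may no longer be possible.

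Separately, the sponsor must reconcile the triggers for early re-start, since they decide who escapes. Protocol 3.1 names a severe flare; protocol 4.4 allows it "if the subject's condition worsens or meets the definition of a severe flare as per the SLE flare index"; Table 2 footnote 16 refers to increased SLE activity as judged by the investigator.

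The cost is some SAP wording and a few extra rows or columns. The drawback is that escapers' data already collected will be sparse.

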13.4.1.1. Treatment Holiday Group

Endpoint	Day 0 Visit Parent Study	Day 0 Visit BEL116027 Study	Week 24/ TX Re-start Visit	Week 52/ Exit/Escape Visit	Week 16 Follow- up Visit	
		Baseline				
Flare, PGA, Prednisone,	N1/A	52-Week Trea	atment Phase	Maintenance		
SLICC	N/A	Holiday Phase	Re-start Phase	Phase	N/A	
	I	Baseline			1	
SS, Auto-antibodies	Pre-Study	52-Week Trea	atment Phase	Maintenance	N1/A	
Immunoglobulins, B-cells [1], BLyS	Phase	Holiday Phase	Re-start Phase	Phase	N/A	
		Baseline	1		1	
Rebound [2]	Pre-Study	52-Week Trea	atment Phase			
	Phase	Holiday Phase	N/A	N/A	N/A	
	L	Baseline			1	
Adverse Events, Lab		52-Week Trea	atment Phase	Maintenance		
Parameters, Vital Signs, Con Meds Immunogenicity [1]	N/A	Holiday Phase	Re-start Phase	Phase	N/A	

N/A = Not Applicable.

[1] Immunogenicity and B-cells may also be collected at the 6-month follow-up visit. The 6-month follow-up visit is not represented in the diagram since it does not define a treatment phase of the study.

[2] Rebound is only assessed up to the Week 24/Treatment re-start visit.

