8.5. Safety Data for Maintenance Phase Subject Profile

AE data, grade 3 or 4 laboratory data, and immunogenicity data will be listed on the subject profile.

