13.4.1.2. Treatment Control Group

Endpoint	Day 0 Visit Parent Study	Day 0 Visit BEL116027 Study [1]	Week 24 Visit	Week 52/ Exit Visit	Week 16 Follow -up Visit				
		Baseline							
Flare, PGA, Prednisone, SLICC	N/A	52-Week Trea	atment Phase	Maintenance Phase	N/A				
Baseline									
SS, Auto-antibodies Immunoglobulins, B-cells [2], BLyS	Pre-Study Phase	52-Week Trea	atment Phase	Maintenance Phase	N/A				
		Baseline		•					
Rebound [3]		52-Week Trea	atment Phase						
	Pre-Study Phase	First 24 Weeks	N/A	N/A	N/A				
		Baseline		•					
Adverse Events, Lab Parameters, Vital Signs, Con Meds, Immunogenicity [2]	N/A	52-Week Trea	atment Phase	Maintenance Phase	N/A				

N/A = Not Applicable.

[1] If the first infusion date differs from the Day 0 visit date, then the first infusion date will be used as the phase cut-point.

[2] Immunogenicity and B-cells may also be collected at the 6-month follow-up visit. The 6-month follow-up visit is not represented in the diagram since it does not define a treatment phase of the study.

[3] Rebound is only assessed up to the Week 24 visit.

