13.11.7. Safety Tables

Safety:	Safety: Tables					
No.	Population	Title	Programming Notes	Priority Headline Results Denoted by H		
Concor	mitant Medicati	ons				
3.1.	ITT	Concomitant Medications by ATC Level 1 and ATC Level 4 Term for the 52-Week Treatment Phase	ICH E3			
Study A	Agent Exposure	9				
3.2.	ITT	Study Agent Exposure (52-Week Treatment Phase)	ICH E3			
SLICC						
3.3.	ITT	SLICC/ACR Damage Index Change from Baseline (52- Week Treatment Phase)	Other/exploratory endpoint			
Advers	e Events		·			
3.4.	ITT	Adverse Events (52-Week Treatment Phase)	Benlysta standard	Н		
3.5.	ITT	Adverse Events by SOC (52-Week Treatment Phase)	Benlysta standard			
3.6.	ITT	Serious Adverse Events by SOC (52-Week Treatment Phase)	Benlysta standard			
3.7.	ITT	Study Agent Related Adverse Events by SOC (52-Week Treatment Phase)	Benlysta standard			
3.8.	ITT	Adverse Events Resulting in Study Agent Discontinuation by SOC (52-Week Treatment Phase)	Benlysta standard			

Safety:	Safety: Tables				
No.	Population	Title	Programming Notes	Priority Headline Results Denoted by H	
3.9.	ITT	Adverse Events by SOC and PT (52-Week Treatment Phase)	ICH E3	Н	
3.10.	ITT	Serious Adverse Events by SOC and PT (52-Week Treatment Phase)	Benlysta Standard	Н	
3.11.	ITT	Study Agent Related Adverse Events by SOC and PT (52-Week Treatment Phase)	ICH E3		
3.12.	ITT	Adverse Events Resulting in Study Agent Discontinuation by SOC and PT (52-Week Treatment Phase)	IDSL	Н	
3.13.	ITT	Adverse Events by PT (52-Week Treatment Phase)	Benlysta Standard		
3.14.	ITT	Serious Adverse Events by PT (52-Week Treatment Phase)	Benlysta Standard		
3.15.	ITT	Study Agent Related Adverse Events by PT (52-Week Treatment Phase)	Benlysta Standard		
3.16.	ITT	Adverse Events Resulting in Study Agent Discontinuation by PT (52-Week Treatment Phase)	Benlysta Standard		
3.17.	ІТТ	Common (>5%) Non-Serious Adverse Events by SOC and PT (52-Week Treatment Phase) (Number of Subjects and Occurrences)	FDAAA, EudraCT		
3.18.	ІТТ	Serious Adverse Events by SOC and PT (52-Week Treatment Phase) (Number of Participants and Occurrences)	FDAAA, EudraCT	Н	
3.19.	ITT	Adverse Events by SOC and PT and Maximum Severity (52- Week Treatment Phase)	IDSL		

Safety:	afety: Tables					
No.	Population	Title	Programming Notes	Priority Headline Results Denoted by H		
3.20.	ITT	Relationship Between System Organ Class and Verbatim Text (52-Week Treatment Phase)	IDSL			

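### The 52-week adverse-event tables stop counting a treatment holiday subject at the Escape visit, although that subject stays in the study and under AE collection

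*SAP*

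**What the plan says.** SAP 13.4.1 states the rule: "Visits, assessments and events will be classified according to the time of occurrence relative to the following cut-point dates for each treatment group". For the TH group (13.4.1.1), the cut-point that closes the 52-Week Treatment Phase and opens the Maintenance Phase is the "Week 52/ Exit/Escape Visit". For the TC group (13.4.1.2) it is the "Week 52/ Exit Visit", and the LTD group (13.4.1.3) has the same end point.

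Escape is the protocol's route for holiday subjects who restart belimumab before Week 24. Section 4.4 gives the trigger as worsening or a severe flare; Section 3.1 names only a severe flare. Section 3.1 continues: "These subjects will then enter the maintenance part of this study by the escape option for ongoing belimumab treatment". The SAP adds: "For the TH group, a subject who re-starts treatment prior to Week 24 will not have a Re-Start phase".

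In SAP 13.11.7, every table from 3.4 to 3.21 is titled for the 52-Week Treatment Phase; the title of Table 3.10, for example, begins "Serious Adverse Events by SOC and PT (52-Week Treatment Phase". Table 3.22, on AEs of special interest by infusion, covers the TH Re-start phase only. For maintenance, SAP 8.5 says: "AE data, grade 3 or 4 laboratory data, and immunogenicity data will be listed on the subject profile". SAP 8.1 plans counts of events and numbers and percentages of subjects, with no subject-time.

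**The concern.** A subject who escapes has not left the trial. Protocol Table 3 schedules AE recording at every 4-week maintenance visit, and Protocol 6.4.7 continues AE collection for TH and TC subjects to the 16-week follow-up contact. The data exist, but the summary tables leave them out.

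The cut is triggered by worsening disease, so it falls on the subjects whose holiday failed. It also treats TH subjects unequally among themselves. AEs after a scheduled restart at Week 24 are in the 52-week tables, while AEs after an earlier, escape-driven restart are not. Protocol 6.4.12 applies the same extended supervision to the first two restart infusions by either route, but the by-infusion reaction summary (SAP 8.2.1.2, Table 3.22) covers only one route.

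Safety is a secondary objective, and the study serves a regulatory commitment on treatment holidays. Because all results are descriptive, these counts and percentages are themselves the safety result.

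**Working it through.** **Inputs.** Enrolled numbers come from SAP 2.3: 12 TH, 29 TC, 39 LTD. Their sum is 12 + 29 + 39 = 80, which reproduces the SAP's stated total. The documents give no figure for AE precision and no escape count. The number of escapes *k*, the escape week *w* and the AE risk are therefore assumptions, shown over a range.

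**Which events are dropped.** An event on a cut-point date counts in the earlier phase (SAP 13.4.1: "then the event will be considered to fall in the previous phase"), so AEs up to and including the Escape date stay in. AEs dated after escape fall in the Maintenance Phase. They are outside Tables 3.4 to 3.21 by phase, and outside Table 3.22 because the subject has no Re-start phase.

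**Loss per escaper** = (52 − *w*)/52:
- *w* = 4: 48/52 = 92.3%
- *w* = 12: 40/52 = 76.9%
- *w* = 20: 32/52 = 61.5%
- limit at *w* = 24: 28/52 = 53.8%

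**Share of planned TH follow-up not tabulated** = *k*(52 − *w*)/(12 × 52), from *w* = 20 to *w* = 4:
- *k* = 0: 0%
- *k* = 1: 5.1% to 7.7%
- *k* = 2: 10.3% to 15.4%
- *k* = 3: 15.4% to 23.1%
- *k* = 4: 20.5% to 30.8%

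**Effect on a crude percentage.** Assume a constant hazard, a true 52-week risk of 50%, three escapes at Week 12, and all 12 subjects in the denominator. The risk counted for an escaper is 1 − 0.5^(12/52) = 14.8%. The TH figure becomes (9 × 50% + 3 × 14.8%)/12 = 41.2%, with no real difference from a group observed in full.

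**Other rates, same assumptions.** At 1 event per subject-year, the 52-week risk is 63.1% and the risk counted for a Week 12 escaper is 20.5%. The TH figure falls to 59.5% with one escaper and 52.5% with three. At 0.2 per subject-year, the 52-week risk is 18.1% and the figure falls to 16.9% or 14.7%.

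**The case against.** Several stronger readings are tempting, and the documents do not support them.

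- *A reader might infer that post-escape events go unreported or appear only in profiles.* They do not. The ITT listings in SAP 13.11.13 carry no phase limit in their titles: 13 (all AEs), 16 to 20 (serious, fatal, related, discontinuation), 22 (special interest) and 25 (infusion reactions). With 12 TH subjects, each event can be found.
- *A reader might infer that the harm of a failed holiday is missed altogether.* AEs that lead up to escape, or fall on its date, are counted. Expected signs of SLE are not AEs unless more severe than expected (Protocol 6.4.2.1). What is missing is AEs with onset after escape, on restarted belimumab.
- *A reader might infer that disease-related truncation occurs only in the TH group.* TC subjects who start prohibited therapy must be withdrawn (Protocol 5.5.2), and their phase ends at Exit; LTD subjects also have withdrawal rules. The difference is that escapers remain under AE collection.
- *A reader might take 41% against 50% as the expected bias.* It is an illustration. It assumes three escapes and a single 52-week TH column over all 12 subjects, and the table shells are not in the document. It amounts to about one subject (6.0 against 4.9 of 12), against a binomial standard error of √(0.5 × 0.5/12), or 14 percentage points. If columns follow the Holiday and Re-start phases, the figure changes, but post-escape events still fall in neither column.

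It can also be said that the disposition and exposure tables (1.5, 1.6, 1.8, 3.2) hint at shorter observation, and that Protocol 8.1.4 promises AE incidence by 6-month interval and allows subject-year rates. Neither AE summary appears in SAP 8.1 or the display list, and SAP Table 2 does not record the omission.

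Finally, ending at escape mirrors the protocol's own move to maintenance, and counting later time is partly a choice of estimand. That has some force, but the TH 52-week phase already includes restarted treatment for those who restart at Week 24.

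**Conclusion.** The point stands as a one-directional undercount in the TH summary tables, confined to AEs starting after escape. With the 12 enrolled subjects as denominator, the rule can only lower the TH percentages. The loss per escaper is known from the visit schedule: 54% to 92% of the window, taking Week 4 as the earliest escape. The total effect cannot be stated because the escape count is not given, and it may be nil. The documents do not support calling the group comparison biased by any particular amount, or the events hidden. This is an inexpensive improvement to the displays that uses data already collected.

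**What to change.** In SAP 13.4.1 and Appendix 11, for Tables 3.4 to 3.21:

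- Keep the Week 52/Exit cut-point for TC, LTD and non-escaping TH subjects.
- Count escaped TH subjects from Day 0 to the target Week 52 day, Study Day 365, or to study withdrawal if earlier. Day 378 should not be used. It is the upper bound of a visit-slotting interval (SAP 13.3.3), 13 days past target. LTD collection stops at the Week 52 visit, so Day 378 would create a new imbalance.
- Split TH events into before and after escape, and show subject-years observed for each group.
- Include escapers' post-restart infusions in the by-infusion reaction summary, Table 3.22.

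The phase-limited version can remain as a secondary display.

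The cost is SAP wording, a date-window change in the AE analysis dataset, and a revised Table 3.22. No new data are needed. There are two downsides, and both can be footnoted. The TH column will include re-treatment time after escape. Scheduled laboratory tests and examinations in maintenance occur only at Weeks 24 and 48 of each cycle (Protocol Table 3), so AE detection after escape is less intensive than in Year 1.
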